12. STATISTICAL CONSIDERATIONS	28
13. REFERENCES.....	30
APPENDICES.....	31
APPENDIX A: PARTICIPANT ELIGIBILITY CHECKLIST	31
APPENDIX B: RECIST 1.1	34
APPENDIX C: IMMUNE-RELATED RESPONSE EVALUATION CRITERIA IN SOLID TUMORS (IMMUNE-RELATED RECIST, IRRECIST)	43
APPENDIX D: TOXICITY MANAGEMENT.....	50
APPENDIX E: ADVERSE EVENTS REPORTING	57
APPENDIX F: PATIENT-REPORTED OUTCOME (PRO) QUESTIONNAIRES	63
APPENDIX REFERENCES.....	92

PROTOCOL SYNOPSIS

TITLE	Phase 2 Study of Ipilimumab Plus Nivolumab in Combination with Cryotherapy in Metastatic or Locally Advanced Soft Tissue Sarcoma
STUDY PHASE	Phase 2
INDICATION	Soft tissue sarcoma
INVESTIGATIONAL PRODUCT OR PROCEDURE	Ipilimumab plus nivolumab in combination with cryotherapy
PRIMARY OBJECTIVE(S)	
 Assess whether the rate of clinical benefit is sufficiently high to merit promise for further study
SECONDARY OBJECTIVE(S)	
 Characterize the 6-month progression-free survival rate Assess whether the treatment yields a reasonably safe and tolerable profile
EXPLORATORY OBJECTIVE(S)	
 Correlate the mutation burden by NGS with response Correlate PDL1 expression with response Correlate tumor infiltrating lymphocytes/macrophages with response
TREATMENT SUMMARY	
 Ipilimumab 1 mg/kg and nivolumab 3 mg/kg every 3 weeks for 4 doses followed by nivolumab 480 mg every 4 weeks until progression or intolerance (maximum 24 months). Cryoablation of at least one tumor mass between Cycle 1 and 2 of above immunotherapy
SAMPLE SIZE	30
STATISTICAL CONSIDERATIONS	
It is anticipated that 3 to 4 subjects will be enrolled per month. It is expected that 12 months will be required to accrue the number of subjects necessary to complete the trial.
 
Treatment response will be assessed for each subject at 16 weeks. The null hypothesis is that the response rate (ie, sum of CR and PR) is $\leq 30\%$, & alternative hypothesis is that the response rate (RR) is $\geq 60\%$. The selection of 60% as a threshold for determining the treatment is worthy of further study is due to recent trials of sarcoma FDA approved drugs showing $\sim 60\%$ PFS rate at 3 months (ie, pazopanib, trabectedin, and eribulin).

STATISTICAL CONSIDERATIONS (continued)	
A Simon-2-stage design will be used to address primary objective. The null hypothesis that the true response rate is 30% will be tested against a one-sided alternative. Our decision rule works as follows. In the first stage, we will accrue and assess 10 subjects. If 3 or fewer subjects (< 30% of 10 subjects) achieve a clinical response, the trial will be stopped for futility. If more than 3 subjects achieve a clinical response, we will enroll and treat an additional 18 subjects. If 12 or fewer of the 28 treated subjects (< 42.8%) demonstrate a clinical response (either CR or PR), we will conclude the treatment is not worthy of further study. If, however, more than 12 of the 28 treated subjects ($\geq 42.8\%$) responds, we will claim the treatment promising. Assuming a true response rate of 60%, we have 90% power to correctly conclude the treatment promising. In contrast, if the true response rate is only 30%, we have a low probability (0.04) of incorrectly continuing to study the treatment.
 
Rates of toxicity will be characterized by level of toxicity as well as by other subject-level characteristics.
 
To address secondary objectives, we will use Kaplan-Meier methods to graphically depict PFS. This tool will also be used to demonstrate survival across various sub-groups of interest. Generalized linear regression methods (with a logit link) will be utilized to characterize relationships between features such as mutation burden, PDL1 expression, and tumor infiltrating lymphocytes and response.

--	--

SCHEMA

LIST OF ABBREVIATIONS AND DEFINITION OF TERMS

ADL	Activities of daily living
AE	Adverse event
BID	Twice daily
BSA	Body surface area
CBC	Complete blood count
CI	Confidence interval
CMAX	Maximum concentration of drug
CNS	Central nervous system
CRF	Case report form
CR	Complete response
CTCAE	Common Terminology Criteria for Adverse Events
DLT	Dose Limiting Toxicity
DSMB	Data Safety Monitoring Board
ECG	Electrocardiogram
GI	Gastrointestinal
Hgb	Hemoglobin
HIV	Human Immunodeficiency Virus
HPF	High-power field
HTN	Hypertension
IRB	Institutional Review Board
irRECIST	Immune-related response evaluation criteria in solid tumors (RECIST)
IV	Intravenous
LLN	Lower limit of normal
MIBI	Multiplexed ion beam imaging
NGS	Next generation sequencing
OS	Overall survival
PLT	Platelets
PD	Progressive disease
PFS	Progression free survival
PR	Partial response
QD	Once daily
RECIST	Response evaluation criteria in solid tumors
RR	Response rate
SAE	Serious adverse event
SD	Stable disease
TTP	Time to progression
ULN	Upper limit of normal
UNK	Unknown
WBC	White blood cell
WHO	World Health Organization

1. OBJECTIVES

1.1. Primary Objectives

- a. Assess whether the rate of clinical benefit is sufficiently high to merit promise for further study**

1.2. Secondary Objectives

- a. Characterize the 6-month progression-free survival (PFS) rate**
- b. Assess whether the treatment yields a reasonably safe and tolerable profile**

1.3. Exploratory Objectives

- a. Correlate the mutation burden by NGS with response**
- b. Correlate PDL1 expression with response**
- c. Correlate tumor infiltrating lymphocytes/macrophages with response**

2. BACKGROUND

Immunotherapy with PD1 antibody, nivolumab, and CTLA-4 antibody, ipilimumab, has been administered safely in subjects with metastatic sarcoma. The combination of these two antibodies improved response rate and overall survival when compared to nivolumab alone (1). Radiation therapy of metastatic melanoma lesions while on immunotherapy has improved response rates both in the irradiated and non-radiated fields (2-5).

We have treated about 40 subjects with metastatic sarcoma with combination ipilimumab and nivolumab in the past 24 months. Many of these subjects had external beam radiation therapy while receiving immunotherapy. However, a minority of subjects were not able to receive radiation due to prior exposure or location of the metastatic lesions. These subjects were treated with cryoablation. We observed tumor responses in both non-ablated and ablated tumors. Theoretically, tumor antigens are released from cryotherapy which can augment the response to immunotherapy. Abdo *et al* proposed that by priming the immune system with CTLA-4 and PD1 inhibitors, cytotoxic CD8+ cell develop after tumor antigens are released by cryotherapy (6), thus facilitating tumor kill by the host's immune system.

In this study, we will prospectively study the response rate, toxicity and outcome in subjects with metastatic sarcoma when treated with cryotherapy while receiving immunotherapy with ipilimumab and nivolumab.

2.1 Study Disease

- a. Metastatic or locally advanced soft tissue sarcomas with at least one tumor area amendable to ablation.
- b. Subjects able to receive immunotherapy (No autoimmune disorders and not on chronic immunosuppression).
- c. Subjects must have archival tumor samples available for Next Generation Sequencing.

2.2 Study Agents and Procedures

- a. Ipilimumab
- b. Nivolumab
- c. Cryoablation

For clinicaltrials.gov compliance

The US Food and Drug Administration (FDA) has not approved ipilimumab nor nivolumab for the treatment of soft tissue sarcoma. An IND will be submitted by the principal investigator of this study; however, it is possible that the FDA may deem this study to be IND-exempt.

2.3 Rationale

Subjects with relapsed or refractory metastatic sarcoma have a dismal prognosis. Response rates to conventional therapy are generally very low, in the range of 10-20%, and new therapeutic approaches are needed for this disease.⁷⁻¹¹

Most subjects with soft tissue sarcomas (STS) are treated with gemcitabine and docetaxel, and some with pazopanib if they tolerate the drug. However, subjects do not have many options following these treatments. Pazopanib will give less than a 10% response rate and has many side effects, and it only improves PFS by 3 months.⁶ Gemcitabine and docetaxel give less than a 20% response rate, and subjects are unable to take these two drugs long-term due to side effects.¹ These are not optimal therapies for STS. This is why we are bringing in immunotherapy and cryoablation therapy, as we hope that they will improve outcome. Based on the encouraging results from the early clinical experience in various types of solid tumors, a clinical study which combines anti-PD-1 and anti-CTLA4 IT with ablation to treat subjects with relapsed or refractory metastatic sarcoma shows great promise to enhance antitumor immune response and improve clinical outcomes.

2.4 Study Design

- The primary purpose for the protocol is treatment
- The interventional model is non-randomized single group
- One intervention arm
 - Ipilimumab 1 mg/kg with nivolumab 3 mg/kg every 3 weeks x 4 doses. (One cycle of treatment is 3 weeks)

- Cryoablation of at least one tumor mass between Cycle 1 to 2 of above immunotherapy
- Maintenance therapy with nivolumab 480 mg every 4 weeks (up to 24 months). (Each cycle of maintenance therapy is 4 weeks).
- Additional ablations are allowed per investigator's discretion
- Subject number: 30
- Primary endpoints
 - Clinical benefit (CR, PR, SD) based on the response evaluation criteria in solid tumors (RECIST) criteria v1.1 and Immune-related RECIST (irRECIST), assessed at 16 weeks.
- Secondary endpoints
 - 6-month progression-free survival
 - Safety and tolerability
 - Correlative measures (See below)

2.5 Correlative Studies ([name] and [name])¹²⁻¹⁴

2.5.1. Archival tumor samples:

Histology, immunohistochemistry for lymphocyte subsets (include multi-marker studies such as MIBI or other) and for Gene Expression profiling with additional analysis of immune subsets by Cibersort and for Gene Expression profiling within the immune cells by CibersortX. The latter dataset can be validated by performing LCM-SMART-3SEQ.

2.5.2 Tumor samples collected throughout study:

Histology, immunohistochemistry for lymphocyte subsets (include multi-marker studies such as MIBI or other) and for Gene Expression profiling (GEP) with additional analysis of immune subsets by Cibersort and for GEP within the immune cells by CibersortX. The latter dataset can be validated by performing LCM-SMART-3SEQ.

2.5.3 Blood collection:

- Determine ctDNA levels
- Gene expression profiling on blood lymphocytes, followed by CibersortX to assess subsets.
 - Gene expression profiling on blood lymphocytes: It is estimated that there will be approximately 20 million white blood cells in 2.5 mL of blood drawn into a PAXgene tube. Two 2.5-mL tubes will be collected at each time point, so approximately 40 million white blood cells will be collected in that volume of blood. Gene expression profiles in blood and tumor may be compared over time.
- Perform flow with purification of T-cells, followed by gene expression profiling

- Perform proteomic analysis for cytokines

3. PARTICIPANT SELECTION AND ENROLLMENT PROCEDURES

3.1 Inclusion Criteria

- 3.1.1 Unresectable or metastatic soft tissue sarcoma
- 3.1.2 ≥ 1 prior systemic therapy for sarcoma, including adjuvant systemic therapy
- 3.1.3 Age ≥ 18 years
- 3.1.4 Life expectancy > 3 months
- 3.1.5 Eastern Cooperative Oncology Group (ECOG) performance status 0 or 1
- 3.1.6 Lab values as below:
 - Absolute neutrophil count (ANC) $\geq 1,000/\text{mm}^3$
 - Platelet count $\geq 75,000/\text{mm}^3$
 - Creatinine $\leq 1.5 \times$ upper limit of normal (ULN) OR calculated (calc.) creatinine clearance $> 45 \text{ mL/min}$ using the lean body mass formula only
 - Total bilirubin $\leq 1.5 \times$ ULN in absence of Gilbert disease (total bilirubin $\leq 3 \times$ ULN with Gilbert); also, if hyperbilirubinemia is clearly attributed to liver metastases total bilirubin $\leq 3 \times$ ULN is permitted
 - AST/ALT $\leq 3 \times$ ULN
 - Thyroid stimulating hormone (TSH) within normal limits (WNL); supplementation is acceptable to achieve a TSH WNL; in subjects with abnormal TSH if free T4 is normal and subject is clinically euthyroid, subject is eligible
- 3.1.7 Any toxic effects of prior therapy (except alopecia) must be resolved to NCI CTCAE, version 5.0, Grade 1 or less
- 3.1.8 Ability to understand and the willingness to sign a written informed consent document
- 3.1.9 Women of childbearing potential (WOCBP) receiving nivolumab must be willing to adhere to contraception for a period of 5 months after the last dose of nivolumab. Men receiving nivolumab and who are sexually active with WOCBP will be instructed and must be willing to adhere to contraception for a period of 7 months after the last dose of nivolumab.

3.2 Exclusion Criteria

- 3.2.1 Prior therapy with ipilimumab or nivolumab, or any agent targeting programmed cell death 1 (PD-1), PD-L1 or cytotoxic T-lymphocyte-associated protein 4 (CTLA-4)

3.2.2 History of the following:

- 3.2.2.1 Active known or suspected autoimmune disease
- 3.2.2.2 Known human immunodeficiency virus (HIV) (Subjects with lymphocytes > 350 cluster of differentiation (CD)4+ cells and no detectable viral load are eligible)
- 3.2.2.3 Active known Hepatitis B. Testing is unrequired in the absence of history.

Hepatitis B can be defined as:

- Hepatitis B surface antigen (HBsAg) > 6 months
- Serum hepatitis B virus (HBV) deoxyribonucleic acid (DNA) 20,000 IU/mL (10^5 copies/mL), lower values 2,000 to 20,000 IU/mL (10^4 to 10^5 copies/mL) are often seen in hepatitis B-e antigen (HbeAg)-negative chronic hepatitis B
- Persistent or intermittent elevation in alanine aminotransferase (ALT)/alanine aminotransferase (AST) levels.
- Liver biopsy showing chronic hepatitis with moderate or severe necroinflammation

- 3.2.2.4 Active known Hepatitis C. Testing is unrequired in the absence of history.

- Hepatitis C antibody (Ab) positive
- Presence of hepatitis C virus (HCV) ribonucleic acid (RNA)

- 3.2.2.5 Known active pulmonary disease with hypoxia defined as:

- Oxygen saturation < 85% on room air or
- Oxygen saturation < 88% despite supplemental oxygen

- 3.2.3 Systemic treatment with either corticosteroids (> 10 mg daily prednisone equivalents) or other immunosuppressive medications within 7 days of registration

- 3.2.4 Received any live/attenuated vaccine (eg, varicella, zoster, yellow fever, rotavirus, oral polio and measles, mumps, rubella (MMRI) within 30 days before initiation of treatment on this protocol.

- 3.2.5 If female, pregnant or lactating. (Women of childbearing potential are required to have a negative pregnancy test within 24 hours prior to the initial administration of study drug)

3.3 Informed Consent Process

All participants must be provided a consent form describing the study with sufficient information for participants to make an informed decision regarding their participation. Participants must sign the IRB approved informed consent prior to participation in any

study specific procedure. The participant must receive a copy of the signed and dated consent document. The original signed copy of the consent document must be retained in the medical record or research file.

3.4 Registration Process

No subject may begin study treatment prior to registration and assignment of a subject identification number.

At registration, Stanford will sequentially assign eligible subjects an identification number. The maximum allowable time between registration and the first administration of study treatment is 14 days. The subject's identification number will be used on all subject-specific Case Report Forms (CRFs) and serious adverse event (SAE) forms. Case report forms will be electronic. Participant information should be entered into OnCore within 5 business days.

3.5 Study Timeline

Primary Completion: Primary completion is the date that the final datum is obtained / expected to be obtained for the primary outcome. The timeframe for primary completion for an individual subject is 16 weeks after initiation of treatment. This datum is expected to be obtained approximately 40 months from the time the study opens to accrual.

Study Completion: The study is expected to reach overall completion (last datum from last subject) approximately 60 months (5 years) from the time the study opens to accrual.

4. TREATMENT PLAN

This is an open-label phase 2 study evaluating the safety and efficacy of ipilimumab/nivolumab in combination with cryotherapy.

The main primary objective of this study is to determine if immunotherapy in combination with cryoablation adds a clinically-significant benefit as measured by the objective response rate (ORR). The response rate will be evaluated by RECIST v1.1 as well as by irRECIST. Imaging by PET-CT or CT scan will be performed at screening, then every 12 weeks \pm 7 days until disease progression. Earlier scans will be performed if clinically indicated. Ablated tumors will not be included as part of the treatment response assessment, ie, disease response; measurable disease; or tumor progression, by either RECIST or irRECIST.

Subjects will receive ipilimumab 1 mg/kg IV over 30 minutes \pm 10 minutes and nivolumab 3 mg/kg IV over 30 minutes \pm 10 minutes every 3 weeks for 4 doses followed by nivolumab 480 mg IV over 30 minutes \pm 10 minutes every 4 weeks until progression or intolerance (maximum 24 months). The standard cycle of investigational agent treatment is considered to be 3 weeks. See Study Calendar at Section 9.

Per protocol cryotherapy (cryoablation) will be performed between investigational agent treatment Cycles 1 and 2 (see Section 5.3). Additional **cryoablation** procedures may be conducted as regular medical care per investigator discretion.

Blood samples will be drawn prior to each immunotherapy administration for routine tests as well as correlative studies. Blood and tissue samples will be retained and used for future research.

After completion of study treatment, a post-treatment biopsy will be obtained if feasible.

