5.3 Cryoablation

Cryoablation of the tumors occur between investigational agent treatment Cycles 1 and 2, and will be performed according to standard procedures. The cryotherapy devices will be FDA-approved cryoablation systems that in current use within the Stanford University Medical Center.

Prior to the cryoablation procedure, the interventional radiologist will review cross-sectional imaging studies to formulate a treatment plan, including identifying the target lesions appropriate for treatment; the number and type of cryoablation probes needed; and optimal percutaneous access approach. As the goal of the cryotherapy is to enhance systemic immunotherapy, the cryoablation will most commonly be subtotal. For lesions that are in close proximity to freeze-sensitive tissues, such as bowel or skin, the cryoablation treatment will be performed with a safe distance (≥ 1 cm) between the edge of the tissue to be frozen (the “iceball”) and the freeze-sensitive tissue.

The cryoablation procedure will be performed with moderate sedation or general anesthesia in a CT procedure room. A limited CT will be obtained and the desired

access sites will be marked on the subject's skin. After sterile preparation of the treatment field and application of local anesthesia, cryoablation probes will be sequentially placed percutaneously into the target lesion(s) using CT and/or ultrasound guidance. After all cryoablation probes are positioned appropriately, cryoablation will be performed with 1 or more freeze-thaw cycles. Iceball growth will be monitored by CT. The probes will then be removed and sterile dressings applied.

In brief, a total of 20 minutes of freezing time will be administered to the tumor in 2 or 3 freeze-thaw cycles. Care will be taken to avoid off-target ablation of sensitive structures such as bowel and skin. The procedures will be performed under either moderate sedation, monitored anesthesia care (conscious sedation), or general anesthesia, depending on the subject's ability to tolerate positioning for the anticipated duration of the procedure. The risks of ablation include hemorrhage, infection, pneumothorax, and injury to off-target structures. With any procedure there is a small risk of death. After ablation, the subject can expect discharge to home within 23 hours in most circumstances.

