- d. Tumor measurements are based on RECIST v1.1 and irRECIST criteria (Appendices C & D). Scans will be done at baseline within 28 days of 1st treatment and then after dose 4 of immunotherapy (W 10 dose). This scan should be done at week 14 ± 1 week and every 12 weeks ± 1 week, once subjects start maintenance nivolumab. Ablated tumors will not be included as part of the treatment response assessment, ie, disease response; measurable disease; or tumor progression, by either RECIST or irRECIST. The baseline measurements will be done before treatment, and follow-up measurements will be done after 4 doses of ipilimumab and nivolumab (12 weeks), then every 12 weeks thereafter. At Investigator's discretion, imaging of known sites of disease is recommended.
- e. Serum β-HCG: Women of child-bearing potential are required to have a negative pregnancy test within 24 hours (eligibility criteria) prior to the initial administration of study drug, then every 3 to 4 weeks (± 1 week) during the study (this test can be omitted if subject is post-menopausal by either surgery or elevated FSH).
- f. ACTH, serum cortisol, TSH, free T4, CRP, ESR.
- g. Archival tumor sample must be available at baseline. All subsequent biopsies will be collected in paraffin for research purposes and standard diagnostics. Blood will be collected at baseline, and prior to treatment dose on weeks 1, 4, 7, 10 and during the off-study visit. Off study visit with a ± 1 week.
- h. Per protocol cryoablation is required to be performed before Week 4 administration of ipilimumab and nivolumab. (between Cycle 1 and Cycle 2), at the discretion of the investigator.
- i. Safety follow-up: After the off-study visit, there will be two additional follow-up phone call/or retrieval of medical records that occur every 35 days ± 1 week to collect information on participants' health status.

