2.1. Assessment of overall tumor burden and measurable disease

To assess objective response or future progression, it is necessary to estimate the overall tumor burden at baseline and use this as a comparator for subsequent measurements. Only subjects with measurable disease at baseline should be included. Measurable disease is defined by the presence of at least one measurable lesion (as detailed above in Section 3).

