2.2. Baseline documentation of 'target' and 'non-target' lesions

When more than one measurable lesion is present at baseline all lesions up to a maximum of five lesions total (and a maximum of 2 lesions per organ) representative of all involved organs should be identified as target lesions and will be recorded and measured at baseline (this means in instances where subjects have only 1 or 2 organ sites involved a maximum of 2 and 4 lesions respectively will be recorded).

Target lesions should be selected on the basis of their size (lesions with the longest diameter), be representative of all involved organs, but in addition should be those that lend themselves to reproducible repeated measurements. It may be the case that, on occasion, the largest lesion does not lend itself to reproducible measurement in which circumstance the next largest lesion which can be measured reproducibly should be selected.

Lymph nodes merit special mention since they are normal anatomical structures which may be visible by imaging even if not involved by tumor. As noted in Section 3, pathological nodes which are defined as measurable and may be identified as target lesions must meet the criterion of a short axis of ≥ 15 mm by CT scan. Only the short axis of these nodes will contribute to the baseline sum. The short axis of the node is the diameter normally used by radiologists to judge if a node is involved by solid tumor. Nodal size is normally reported as two dimensions in the plane in which the image is obtained (for CT scan this is almost always the axial plane; for MRI the plane of acquisition may be axial, sagittal or coronal). The smaller of these measures is the short axis. For example, an abdominal node which is reported as being 20 mm \times 30 mm has a short axis of 20 mm and qualifies as a malignant, measurable node. In this example, 20 mm should be recorded as the node measurement. All other pathological nodes (those with short axis ≥ 10 mm but < 15 mm) should be considered non-target lesions. Nodes that have a short axis < 10 mm are considered non-pathological and should not be recorded or followed.

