2.3.1. Evaluation of target lesions

Complete Response (CR): Disappearance of all target lesions. Any pathological lymph nodes (whether target or non-target) must have reduction in short axis to < 10 mm.

Partial Response (PR): At least a 30% decrease in the sum of diameters of target lesions, taking as reference the baseline sum diameters.

Progressive Disease (PD): At least a 20% increase in the sum of diameters of target lesions, taking as reference the smallest sum on study (this includes the baseline sum if that is the smallest on study). In addition to the relative increase of 20%, the sum must also demonstrate an absolute increase of at least 5 mm. (Note: the appearance of one or more new lesions is also considered progression).

Stable Disease (SD): Neither sufficient shrinkage to qualify for PR nor sufficient increase to qualify for PD, taking as reference the smallest sum diameters while on study.

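### Ablated tumours leave the response assessment, but eligibility does not require a measurable lesion that stays unablated, and the exclusion has no time limit

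*Combined protocol and SAP*

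**What the plan says.** **The ablation.** Section 2.4 has at least one tumour mass ablated between Cycles 1 and 2. Section 9, footnote h, says: "Per protocol cryoablation is required to be performed before Week 4 administration of ipilimumab and nivolumab".

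**The exclusion.** Section 4 says: "Ablated tumors will not be included as part of the treatment response assessment, ie, disease response; measurable disease; or tumor progression". This applies under both RECIST 1.1 and irRECIST, and Section 9, footnote d, repeats it. Neither place limits the rule to the protocol ablation or says from when a lesion leaves the assessment. Sections 2.4 and 4 allow further ablations at the investigator's discretion. Section 4.1, by contrast, limits palliative radiation to non-target lesions.

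**Eligibility.** The disease criterion in Section 3.1, repeated in the Appendix A checklist, is "Unresectable or metastatic soft tissue sarcoma". Section 2.1 adds an area that can be ablated. The nearest rule on measurability is in Appendix B, Section 2.1: "Only subjects with measurable disease at baseline should be included".

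**Target lesions.** Footnote d says: "The baseline measurements will be done before treatment". Appendix B, Section 2.2, selects targets mainly by size and does not say to avoid the lesion that will be ablated. A PR requires "At least a 30% decrease in the sum of diameters of target lesions" (Appendix B, Section 2.3.1).

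**Decision rule.** Section 12 stops for futility at 3 or fewer responders of 10, and calls the treatment promising with more than 12 responders among 28 treated subjects. It states 90% power at a 60% response rate and a type I error of 0.04 at 30%. It has no rule for subjects who cannot be assessed.

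**The concern.** The plan removes at least one lesion per subject from the assessment but does not make sure that a measurable one is left. Locally advanced disease is within scope (Section 2.1), so subjects with a single measurable mass are foreseeable. Such a subject can be enrolled and treated exactly as the plan says and then have no target lesion in which a PR could be seen. The denominator is treated subjects, so each one would most likely sit in it as a non-responder. That costs power and makes a wrong futility stop after 10 subjects more likely.

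The secondary issue runs the other way. Because the exclusion has no time limit, a lesion ablated later also drops out, after the investigator has seen how it behaves. Section 5.3 expects ablation to be subtotal in most cases, so viable tumour can regrow in a lesion that no longer counts. In an open-label single-arm trial this can bias the Kaplan-Meier curve for PFS, and possibly response, in favour of the treatment.

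**Working it through.** **1. Does any passage close the gap?**
- Sections 3.1 and 3.2 and the checklist contain no measurability criterion.
- Appendix B, Section 2.1, applies at baseline. The lesion to be ablated is still intact then and satisfies it.
- Appendix B, Section 1.1.3, leaves it to the protocol to say when locally treated lesions are measurable. Section 4 says that ablated tumours are excluded, but not that another measurable lesion must exist.
- With no target lesion left, PR is impossible. Non-target and new lesions can still be followed, so PD remains possible, as does CR if all non-target disease disappears. The nearest row of Table 1 in Appendix B (targets not all evaluated, non-target disease not progressing, no new lesion) gives NE.

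**2. The plan's own figures.** Inputs from Section 12: n1 = 10, continue if X1 ≥ 4; n = 28, promising if the total is ≥ 13.

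P(promising) = Σ over x = 4 to 10 of P(Bin(10, p) = x) × P(Bin(18, p) ≥ 13 − x)

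- p = 0.60: 0.912 (stated 90%).
- p = 0.30: 0.042 (stated 0.04).

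The design is calculated correctly.

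**3. Effect of k unassessable subjects.** Assumptions:
- (a) They count as non-responders, with no CR through non-target disease.
- (b) The 60% or 30% rate applies to the assessable subjects.
- (c) The endpoint is CR plus PR.
- (d) The k subjects fall at random over the two stages.

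With k1 of them in stage 1 and k2 = k − k1 in stage 2, and the cut-offs unchanged:

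S(k1, k2) = Σ over x = 4 to 10 − k1 of P(Bin(10 − k1, p) = x) × P(Bin(18 − k2, p) ≥ 13 − x)

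This is averaged with weights C(10, k1) C(18, k2) / C(28, k). For k = 1 and p = 0.60: (18/28) × 0.8933 + (10/28) × 0.8576 = 0.881.

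| k among 28 | Power at 60% | Type I error at 30% |
|---|---|---|
| 0 | 0.912 | 0.042 |
| 1 | 0.881 | 0.031 |
| 2 | 0.840 | 0.022 |
| 3 | 0.788 | 0.015 |

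As a cross-check with a share instead of a count: if 10% of subjects are unassessable, the effective rate is 0.60 × 0.90 = 0.54, and power is 0.785.

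**4. Futility stop at stage 1, rate 60%.**
- None unassessable among the first 10: P(Bin(10, 0.6) ≤ 3) = 0.055.
- One: P(Bin(9, 0.6) ≤ 3) = 0.099.
- Two: P(Bin(8, 0.6) ≤ 3) = 0.174.

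**5. Later ablations.** No figure can be derived. The documents give neither the frequency of later ablations nor a rule for the sum of diameters once a target lesion is excluded.

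**The case against.** **The passages may already imply the requirement.** Section 4 and footnote d exclude ablated tumours from measurable disease as well as from response, and Appendix B admits only subjects with measurable disease. Together these can be read to demand a second lesion. This is a fair reading, and a reader should not infer that measurable disease is required nowhere. But the inference is never stated, and the checklist completed before registration does not carry it.

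**The power loss depends on what the 60% means.** If 60% is the rate over all treated subjects, the unassessable ones are already inside it and power stays at 0.912. For one such subject, the assessable rate would then have to be 0.60 × 28 / 27 = 62.2%. This objection stands as a condition on the figures. So does the fact that Sections 2.4 and 12 also describe the endpoint as CR, PR or SD; the calculation covers CR plus PR only. That wider endpoint does not clearly rescue the subject, because NE is not SD.

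**Later ablation and false responses.** A reader might infer that ablating a growing target lesion turns stable disease into a PR. The documents do not establish this. It would require the baseline sum to be recalculated without that lesion, and no passage says so. Appendix B takes the baseline sum as reference and usually calls a partial set of measurements NE. Progression already documented before the ablation still counts. What stands is that the text is silent, so favourable handling is possible.

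**Ablated lesions are hard to read.** Appendix B warns that locally treated lesions are usually not measurable and that necrosis or cystic change can resemble progression. Simply keeping every later-ablated lesion in the assessment could create false progression. The fix has to allow for this.

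**Conclusion.** The gap is real. Following the plan as written, a subject can be enrolled who cannot show a PR. A single such subject takes the calculated power from 0.912 to 0.881, below the stated 90%, and three take it to 0.788. These figures hold if unassessable subjects count as non-responders on CR plus PR and if 60% is the rate among assessable subjects. The number of such subjects is unknown, and 1 to 3 is an assumed range.

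The direction is conservative. Type I error falls, so this part gives no ground to infer a raised risk of a false positive result. The risk is that an active treatment is dropped.

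The unlimited exclusion of later-ablated lesions is secondary. It can favour PFS, and possibly response, but the size cannot be stated from the documents. The plan should be changed on both counts; neither shows an error in the two-stage design itself.

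**What to change.** **Eligibility and target lesions**
- Add to Section 3.1 and Appendix A: *at least one RECIST 1.1 measurable lesion not designated for, and not to be substituted into, the protocol cryoablation*.
- Record the designated lesion or lesions at baseline, and choose target lesions only from the others.
- State in Section 12 that a treated subject without an assessable response counts as a non-responder.
- Optionally, use another term in Section 5.3, where the radiologist's review includes "identifying the target lesions appropriate for treatment", since that is also the RECIST name for the measured lesions.

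**Later ablations (Section 4 and Section 9, footnote d)**
- Limit the exclusion to lesions ablated as the protocol cryoablation between Cycles 1 and 2.
- State that removing a later-ablated lesion from the sum cannot by itself create a response, and that its measurements before ablation stay in the assessment.
- State that later change in such a lesion counts as progression only when it is unequivocal and not attributable to the ablation, in line with the cautions in Appendix B.
- Add a PFS sensitivity analysis that counts later ablation of a growing or new non-designated lesion as an event.

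**Cost.** One eligibility line in two places, one baseline CRF field, a few sentences in Sections 4, 9 and 12, and one extra analysis. The lesion to be ablated has to be named provisionally at baseline. Some patients with a single measurable lesion become ineligible, and the reported response and PFS figures may be slightly lower. The changes concern who is eligible and how lesions are counted; the clinical choice of which lesions to ablate is unchanged.
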